
A2 Primary Hypothesis

Hypothesis 1: Patients in the intervention arm will have significantly fewer med errors and adverse drug events, as compared to the usual care arm, at the end of the 12-month study

Hypothesis 2: The intervention arm will have significantly fewer healthcare encounters (clinic visits, ED visits and hospitalizations), leading to reduced costs, as compared to the usual care arm, at the end of the 12-month study

A3 Purpose of the Study Protocol

Due to the complexities and toxicities associated with their immunosuppressive medication regimens, kidney transplant recipients are at high-risk of developing medication safety issues which can lead to hospitalization, increased healthcare expenditures and ultimately, graft loss. Founded on preliminary information, the use of pharmacists and mHealth technology provide a promising and innovative approach to

[figure not shown]
improve medication safety in high-risk patients. The ultimate goal of this research is to demonstrate how patients, pharmacists and technology can work hand-in-hand to optimize medication-related outcomes and reduce healthcare expenditures.

B Background

B1 Prior Literature and Studies

Within kidney transplantation, despite dramatic improvements in acute rejection rates, long-term graft survival has not improved to nearly the same degree. Since 2003, there has been a 50% reduction in acute rejection rates; yet, during this same time period, the kidney allograft half-life has only increased by a modest 0.6 years.(3, 4) The most recent report from the Scientific Registry of Transplant Recipients (SRTR) demonstrates a historically low one-year acute rejection rate of <10%, with a suboptimal five-year graft survival rate of 70%.(1) Medication safety issues, which encompass both medication errors and adverse drug events, are a predominant cause of deleterious clinical outcomes in kidney transplant recipients; most notably, graft loss.

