- Determine the incidence, severity and etiologies of med errors and adverse drug events in kidney transplant recipients and compare these between the intervention and control cohorts.

C2 Secondary Aims

- Measure the total resources utilized (hospital, outpatient, staff effort) to provide care and compare these between the intervention and control cohorts.
- Measure the impact of med errors and adverse drug events on clinical outcomes, including acute rejections, infections, graft loss and death (exploratory aim)

D Study Design

D1 Overview or Design Summary

TRANSAFE Rx is a 12-month, parallel two-arm, 1:1 randomized controlled clinical trial, involving 136 participants (68 in each arm) and measuring the clinical and economic effectiveness of a pharmacist-led intervention, which utilizes an innovative mHealth application to improve medication safety and health outcomes, as compared to usual post-transplant care. The planned study design and interventions of this project were developed from the aforementioned foundational studies. These preliminary studies provided insight into interventions that were clinically effective, efficiently implementable, had a high-rate of patient acceptability and were capable of being scalable to a wide-array of patient populations. It is within this framework that the investigators have designed the TRANSAFE Rx study.

D2 Subject Selection and Withdrawal

2.a Inclusion Criteria

- 1) Kidney transplant recipient between 6 and 36 months post-transplant
- 2) At least 18 years of age
- 3) Transplant MD agrees that patient is eligible to participate

2.b Exclusion Criteria

- 1) Multi-organ recipient
- 2) Patient is incapable of:
 - a. Measuring their own blood pressure
 - b. Measuring their own glucose (if subject has diabetes)
 - c. Self-administering medications
 - d. Speaking, hearing and reading English
 - e. Utilizing the mHealth application, after training

2.c Ethical Considerations

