To assess for adverse drug events, the research coordinator will review patient symptomology, vital signs and laboratory values. The research coordinator will be trained by the study pharmacists in identifying medication errors and adverse drug events, determining causality and grading the severity. To ensure objectivity and consistency in recording these events across both study cohorts, a number of safeguards will be instituted. First, the study investigators will utilize the same research coordinator to record all medication errors and adverse drug events. Second, this research coordinator will be completely independent of the telehealth intervention that is being performed and will be blinded to the patient’s randomized group. Third, only the medication errors and adverse drug events recorded by this research coordinator will be

used for data analysis. Finally, these patient assessments will be followed by an independent assessment by a clinical transplant pharmacist that is not associated with delivering the study intervention. This will ensure that event rates are not biased towards a higher capture rate in the intervention cohort, which will be receiving more intense scrutiny of their medication regimens by a clinical pharmacist.

E4 Study Outcome Measurements and Ascertainment

The primary outcome measure of this study will be the incidence and severity of medication errors and adverse drug events, which will be identified, categorized and compared between the intervention and control cohorts as detailed above and in the following sections. The exploratory outcome measures of this study are to compare the incidence and severity of acute rejections, infections, graft function, graft loss and death between research cohorts and measure the association between medication safety issues and these events. Demonstrating improvements in acute rejections, infections, graft loss or death within the intervention group will provide the data needed to design a larger, multicenter study (through dissemination efforts detailed at the end of this proposal). Additional data that will be gathered includes patient surveys to capture measures of sociodemographics, health literacy, depression, social support and trust. These are important variables that may modify or confound the impact of the intervention.

Study endpoint definitions and assessment plan:

The following will be used to define and capture data and events within this study:

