Based on previous studies conducted by our research collaborative, we estimate that approximately 64% of kidney transplant recipients in the control group will experience a medication error during the one year study (defined using the Overhage criteria).(1, 2) Our previous research demonstrates that pharmacist-led initiatives can reduce these medication errors by approximately 50%.(3, 4) Using these estimates, enrolling 104 participants (52 in each cohort), will provide 92% power in detecting a statistically significant difference in medication error event rates, with a two-tailed $\alpha=0.05$. We will also have 94% power (two-tailed, $\alpha=0.05$) to detect a 33% reduction in significant adverse drug events (CTCAE grade 3 or higher), given an estimated incidence rate of 87% in the control cohort and the strong association between medication errors and adverse drug events.(2, 5) From previous analyses, we expect that the control cohort will have a mean of 18.4 ± 2.6 healthcare encounters (clinic visits, acute care/ER visits and hospitalizations), during the one year study. We estimate the intervention group will see an 8% absolute reduction in total encounters, to a mean 17.0 encounters, with an estimated 33% relative reduction in the mean number of hospital readmissions (1.2 vs. 0.8, respectively).(2) Given these estimates (two-tailed, $\alpha=0.05$), enrolling 52 patients in each arm will provide 80% power to detect a statistically significant difference. It is estimated that the intervention will also produce a mean cost savings of at least \$2,489 per patient (\$7,658 in the control cohort and \$5,169 in the intervention cohort, with σ estimated at \$4,530).(2) This study is expected to have >80% power to detect a statistically significant difference in total post-transplant costs between cohorts, given these estimates.

For the exploratory outcomes of acute rejection, infections, graft function, graft loss and death, this study is not powered to detect statistically significant differences in these clinical events between groups. However, we expect to demonstrate meaningful clinical signals, particularly with a reduction in acute rejection. Our previous study demonstrated an acute rejection rate that was 1.8 times higher in patients experiencing a significant medication error (13.7% vs. 7.7%, respectively).(2) Thus, we expect an overall acute rejection rate of 12% in the control cohort and 9% in the intervention cohort,

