corresponding with a 25% relative reduction in acute rejection rates. Based on previous randomized controlled trials conducted within the study institution, we expect to maintain an 85% retention rate.(6) We will adjust our total sample-size to 136 patients (68 in each cohort) to account for dropouts, thus maintaining adequate sample-size to produce at least 80% power to detect statistically significant differences in the primary outcome measures.

F2 Interim Monitoring and Early Stopping

The safety officer and statistician will meet at the following seven pre-designated study milestones: each time 34 patients have received at least six months of study follow-up care (four meetings), once 68 patients have completed the study (one meeting), once 102 patients have completed the study (one meeting), and at study close-out. The team will also meet on an as needed basis for any unexpected serious adverse events or significant study findings. Data will be provided at these meetings by the investigators on key variables that may indicate harm, including significant medication safety events leading to hospitalization. Study patient clinical events, including hospitalizations, emergency room visits, acute rejections, life-threatening infections, graft loss and patient death will also be reviewed during these sessions. The biostatistician will evaluate confidentiality and integrity of the database, and the procedures for recording and storing confidential files. The safety officer will also review the elements of the research plan to deal with emergencies. At the conclusion of these meetings, the recommendations of the safety officer will be reviewed and the PI and co-investigators will take appropriate corrective actions as needed.

The safety officer will have the authority to halt the trial if he/she perceives that harm is occurring due to the interventions.

F3 Analysis Plan

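### Hypothesis 2 (encounters and costs) is headed primary in A2 but is secondary in C2 and absent from the primary outcome in E4, and no testing rule settles which status governs a significant result.

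*Combined protocol and SAP*

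**What the plan says.** All references are to the combined protocol and SAP.

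- **A2.** Under the heading "A2 Primary Hypothesis" the plan lists two hypotheses. The first concerns medication errors and adverse drug events (ADEs). The second reads "Hypothesis 2: The intervention arm will have significantly fewer healthcare encounters (clinic visits, ED visits and hospitalizations), leading to reduced costs".
- **C2, Secondary Aims.** "Measure the total resources utilized (hospital, outpatient, staff effort) to provide care and compare these between the intervention and control cohorts".
- **E4.** "The primary outcome measure of this study will be the incidence and severity of medication errors and adverse drug events". The exploratory label there covers rejection, infection, graft function, graft loss and death. Encounters and costs are defined in items 7 and 8 but given no rank.
- **F1.** Encounters are planned from "a mean of 18.4 ± 2.6 healthcare encounters" in the control arm to 17.0 in the intervention arm. At two-sided 0.05, "enrolling 52 patients in each arm will provide 80% power to detect a statistically significant difference". Costs get their own power statement (above 80%), with no alpha restated. Readmissions (1.2 against 0.8) appear beside the encounter estimate without an SD, alpha or power of their own. F1 closes by promising "at least 80% power to detect statistically significant differences in the primary outcome measures", without listing those measures.
- **F3 and F4.** Tests and models are named by type of variable. There is no significance level, order, gate, adjustment or definition of trial success.

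**The concern.** The same family of outcomes is primary in one section, secondary in another and unranked in a third. Suppose errors and ADEs show no difference and costs give p = 0.04. A reader of A2 could report that a primary hypothesis was confirmed. A reader of C2 and E4 would report a trial that missed its primary outcome, with one nominal secondary result. Nothing in F1 to F4 decides between them, so the choice could be made after the data are seen.

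A2 is not an isolated slip. The abstract (A1) and the rationale (B2) also place reduced resource use in the study's main goal and central hypothesis.

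**Working it through.** **1. The plan's own power figures (F1, 52 per arm, two-sided 0.05).** Power ≈ Φ(δ / (SD·√(2/n)) − 1.96).

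- Encounters: δ = 18.4 − 17.0 = 1.4; SE = 2.6·√(2/52) = 0.510; 1.4/0.510 = 2.746; Φ(0.786) = 78.4% (77.6% by noncentral t). An exact 8% fall (1.472) gives 82.3%. The stated 80% is reproduced within two points.
- Costs: SE = 4,530·√(2/52) = 888; 2,489/888 = 2.80; Φ(0.842) = 80.0% (79.3% by noncentral t).
- Errors, 64% against 32%: 91.6%, stated 92%. ADEs, 87% against 58.3%: 91.9% to 93.4% by method, stated 94%.

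So F1 powers four outcomes within A2: two under Hypothesis 1 and two under Hypothesis 2.

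**2. Family-wise error if any one significant result counted as success.** This rule is an assumption, and so are the correlations, which the documents do not give. With k tests at two-sided 0.05 and common correlation ρ, take Z = √ρ·S + √(1−ρ)·E for each test. The error is

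1 − ∫ φ(s)·[Φ((1.96 − √ρ·s)/√(1−ρ)) − Φ((−1.96 − √ρ·s)/√(1−ρ))]^k ds,

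which is 1 − 0.95^k at ρ = 0.

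| ρ | k = 2 (encounters, costs) | k = 4 (errors, ADEs, encounters, costs) |
|---|---|---|
| 0 | 9.75% (1.95 × 5%) | 18.5% (3.7 ×) |
| 0.5 | 9.1% (1.8 ×) | 15.6% (3.1 ×) |
| 0.8 | 7.8% (1.6 ×) | 11.4% (2.3 ×) |
| 0.9 | 7.0% (1.4 ×) | 9.4% (1.9 ×) |

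**3. The opposite rule.** If every test had to be significant, the error could not exceed that of a single test, 5%. For two tests it is 0.05² = 0.25% at ρ = 0 and 2.2% at ρ = 0.8.

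**4. What an optional fixed sequence would cost.** Marginal powers at 52 per arm: errors 0.92 and ADEs 0.94 (F1), encounters 0.776 and costs 0.793 (step 1). Probability that every test up to and including the one named is significant:

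| Sequence | ρ = 0 | ρ = 0.8 |
|---|---|---|
| errors → encounters | 0.92 × 0.776 = 71.4% | 76.5% |
| errors and ADEs → encounters | 0.92 × 0.94 × 0.776 = 67.1% | 76.0% |
| errors → encounters → costs | 0.714 × 0.793 = 56.6% | 70.5% |
| errors and ADEs → encounters → costs | 0.671 × 0.793 = 53.2% | 70.3% |

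The ρ = 0.8 column uses the same one-factor model, with normal means set to give these marginal powers.

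**The case against.** The strongest reply is that C1, C2 and E4 agree on what is primary, and that the conflict comes from one introductory heading written in the singular. The goals are also phrased as a chain: fewer safety events lead to lower resource use, and fewer encounters lead to lower costs. Read that way, both links would have to be shown and the error rate would not rise. This stands as far as it goes. The plan never says that one result is enough, so no inflated error rate can be read off as fact. It never says that both are needed either, and the ambiguity remains.

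Four stronger readings are tempting, and the documents do not support them.

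- **A single multiplier such as 1.8 to 3 times the stated error.** It needs a test count, correlations and a success rule that the plan does not give. Its upper end also depends on counting the Hypothesis 1 tests.
- **F1 itself makes encounters and costs primary, because only they sit near the 80% floor.** Errors and ADEs, at 92% and 94%, already satisfy the promise and account for the plural.
- **Hypothesis 2 has no contrast at all, or readmissions are a third confirmatory test.** F1 gives a mean and SD for total encounters. Readmissions have no SD, alpha or power there, and the categories in E4 item 7 classify the encounters without being designated as tests.
- **A gatekeeping sequence is required.** Secondary outcomes may be reported without one if no confirmatory claim is made for them.

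**Conclusion.** The contradiction between A2 and C2/E4 is real and affects what the trial may conclude. As written, a significant encounter or cost result could be presented as a confirmed primary hypothesis even if errors and ADEs do not differ.

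The numerical size is conditional. Under an any-one-wins rule it is about 1.4 to 2.0 times 5% for the two powered Hypothesis 2 contrasts, and about 1.9 to 3.7 times for all four powered outcomes, at correlations from 0.9 to 0. Under an all-must-be-met rule there is no inflation. Each single test keeps its 5% in either case. Alpha 0.05 is explicit for encounters and only implied for costs. The point should be settled before analysis, but it does not call the design or the sample size into question.

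**What to change.** - **A2:** label Hypothesis 1 primary and Hypothesis 2 secondary, matching C2 and E4.
- **F1:** state that the primary outcome measures are medication errors and ADEs.
- **F3:** name total encounters over 12 months as the main Hypothesis 2 contrast, and say which visit types it sums, since A2 lists three and E4 item 7 four. Report costs, readmissions and the encounter categories as secondary estimates with 95% confidence intervals. State that no Hypothesis 2 result will be presented as a primary success.

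This changes wording only, with no extra patients or data. The downside is that a positive encounter or cost result can no longer be claimed as primary.

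A fixed sequence (Hypothesis 1, then total encounters, then costs) is optional, for use if the sponsor wants confirmatory secondary claims. It first needs a stated success rule for Hypothesis 1, which the plan lacks. Its price should also be reported: at 52 per arm, encounter power falls from 78% to about 67% to 77%, and cost power from 79% to about 53% to 71%, for correlations 0 to 0.8.

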Whether a patient is in the intervention group or the control will be by random selection using a random number generator in a simple blocked manner (blocks of 8).

Blinding:

This is an open-label study, so subjects and the research team will be aware of the study assignment. Due to the nature of the intervention, blinding of the subject and research staff is unable to be performed. In order to minimize bias, data for outcomes will be collected by a blinded study coordinator.

2.f Risks and Benefits

There are minimal risks to patient safety during the completion of this study within the intervention arm and no risks with regards to study interventions within the control arm. This study will not involve requiring patients to take any experimental medications. All patients, regardless of randomization will receive standard usual care as part of this study. Any adjustments or changes made to the patient's medication regimen in the intervention group will be approved by a transplant physician. There will be increased monitoring and scrutiny of patient's home blood pressures, glucoses and medication regimens. All documented medication errors and adverse drug events will be identified by a blinded research coordinator at the same frequency and methodology across intervention and control patients. This will minimize the likelihood of identifying higher rates of medication safety issues in the intervention group. The risk associated with the intervention arm is in loss of patient confidentiality, which will be mitigated through the use of HIPPA compliant data encryption on mobile devices and storage of PHI on password protected databases behind the MUSC firewall.

Although it is expected that this will improve medication safety, it may also increase stress on patients and increase the potential of identifying false positive information. We will minimize the risk of this causing harm to study patients by ensuring all data is closely monitored by a highly trained clinical pharmacist. All interventions made based on this will be reviewed and approved by a transplant physician.

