The clinical transplant pharmacist will be alerted by the patient if there are medication changes made by outside providers, by way of making adjustments to the medication regimen in the mobile app. At this point, the patient will be contacted to evaluate the medication change and determine if the adjustment to the regimen is safe and effective. If the pharmacist deems this change to be of concern, they will work with the patient and transplant physician to alter the regimen in an appropriate manner. In addition, the pharmacist will be alerted if the patient has evidence of significant nonadherence ($\geq 20\%$ missed self-reported medication doses in the course of a week), if they have blood pressure or glucose values that fall into critical ranges or if there are alarming trends in their readings or symptom assessments from surveys. Upon receiving these alerts, the pharmacist will communicate with the patient, determine the root cause and coordinate care with other care providers as delineated at the bottom of Figure 4.

[figure not shown]
During televisit encounters, the transplant pharmacist will conduct a thorough medication review, evaluate for signs and symptoms suggestive of medication safety issues, screen for drug-drug and drug-disease interactions and provide recommendations to resolve identified issues to the patient and/or provider, when applicable. The clinical pharmacist will be alerted and evaluate each patient when making a transition of care (inpatient admission or discharge) to ensure accurate medication regimens are communicated to accepting teams and to the patient. The same ambulatory EPIC note template that is used by the clinical pharmacist during the usual care visits will be utilized for documentation during these telehealth encounters. EPIC is the inpatient and ambulatory EHR utilized within the study institution. The process used to resolve medication safety issues during distant monitoring is outlined in Figure 4. Once the clinical pharmacist identifies an issue, they will develop a management plan using the algorithm detailed in Figure 5, discuss the recommendations with the providers, agree on a plan, and implement the plan with direct patient follow-up. The algorithm in Figure 5 encompasses the major medication safety issues, including side effects, adherence, drug interactions and less than optimally controlled comorbid disease states.

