6. Graft failure will be defined as return to chronic dialysis, transplant nephrectomy, retransplantation or death. The study coordinator capturing clinical event data, different from the coordinator capturing medication error and adverse drug event data (to ensure independence is maintained), will review the medical record at regular intervals to determine if a study patient has developed graft failure. The timing and cause of each graft loss will be recorded for comparative analysis. Patient death will also be captured in a similar fashion, with timing and cause recorded as well.

7. Healthcare encounters will be defined as any direct encounter (face-to-face) between the study patient and a physician or advance practice provider (APP) occurring within a licensed healthcare facility and occurring during the 12-month study. These encounters will be categorized as ambulatory clinic visits, ambulatory procedure visits, acute care/emergency room visits and hospitalizations. Hospitalizations will be defined as an admission to a hospital with at least one overnight stay. Length of stay within the hospital for readmissions will also be captured. Healthcare encounters will be captured through direct study subject interviews with patients at bimonthly intervals.(36) The study coordinator will record all healthcare encounters that have occurred. If the patient has a health care encounter outside of the study institution, the research coordinator will document the type of encounter to estimate costs, as detailed below.

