8. Costs associated with care will be assessed based on data from hospital accounting at the study institution, once the study is completed. Costs will be measured from the time of randomization up until the end of the 12-month follow-up period. Analyses will include all costs associated with inpatient and outpatient care, including hospitalizations, ambulatory care visits, ambulatory procedure visits, acute care/emergency room visits and laboratory assessments. Costs uniquely associated with the intervention group will include the costs of the devices and data plan provided to the patients, time necessary for training patients on use of the technology and research pharmacist time associated with the intervention. Total costs will be calculated for each cohort. These data will be electronically captured by providing a list of patient's MRNs to hospital accounting after the completion of the study to allow for accurate and complete billing information to accrue. Costs associated with healthcare encounters that occur outside the study institution will be estimated by acquiring information from the patient regarding the type of encounter and using this data to estimate cost based on cost/charge ratios from the study institution. This will be a costs - consequences analysis (CCA) using cost effectiveness methodology, taken from the societal perspective.

F Statistical Plan

F1 Sample Size Determination and Power

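### C2 promises a between-arm comparison of staff effort, but the E4 cost list omits the transplant-physician review that 2.f requires, so the net saving is likely overstated by the value of that time

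*Combined protocol and SAP*

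**What the plan says.** - **Aim (C2).** The secondary aim is to "Measure the total resources utilized (hospital, outpatient, staff effort) to provide care and compare these between the intervention and control cohorts". Staff effort stands beside hospital and outpatient resources as a separate thing to compare.
- **Cost list (E4 item 8).** Inpatient and outpatient costs come from hospital accounting in both arms. For the extra inputs, item 8 says: "Costs uniquely associated with the intervention group will include the costs of the devices and data plan provided to the patients", and then adds "time necessary for training patients on use of the technology and research pharmacist time associated with the intervention". No other staff time is named. The analysis declares a societal perspective.
- **Physician role (D2, 2.f).** Changes to the "medication regimen in the intervention group will be approved by a transplant physician". On the monitoring data more generally: "All interventions made based on this will be reviewed and approved by a transplant physician".
- **Workflow (D3, 3.a).** Once an issue is found, the pharmacist is to plan its management, "discuss the recommendations with the providers, agree on a plan, and implement the plan with direct patient follow-up".
- **Encounters (E4 item 7).** A healthcare encounter is "any direct encounter (face-to-face) between the study patient and a physician or advance practice provider (APP", in a licensed facility. E2 says the care added in the intervention arm is all remote.
- **Usual care (D3, 3.a).** Both arms receive the same usual care. It includes pharmacist work: "The same ambulatory EPIC note template that is used by the clinical pharmacist during the usual care visits" also serves for the televisits. Item 8 does not name usual-care pharmacist time.

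**The concern.** Hypothesis 2 predicts lower costs from an intervention that adds remote professional work in the hope of avoiding visits and admissions. The comparison is only as good as its count of that added work. Item 8 counts the pharmacist's share and leaves out the physician's share, although 2.f makes the physician's approval part of how the intervention is delivered. A saving reported on this basis would be larger than the net saving by whatever the physician's time is worth.

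The aim also asks for a comparison, yet item 8 describes no measure of staff effort for control patients and no method of recording or valuing minutes in either arm. A reader of the final report could not tell whether staff effort was compared or only partly costed in one arm.

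**Working it through.** **1. Can the physician time enter the cost total by any route in the plan?**

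| Route | Does it capture remote physician review? |
|---|---|
| Intervention-only list, item 8 | Not named; only devices, data plan, training time and research-pharmacist time are |
| Encounters, item 7 | No; face-to-face contact between patient and physician or APP is required |
| Hospital accounting, item 8 | Only if it generates a cost or billing record; the documents do not say that it does |

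No route is certain to capture it. If c is the uncounted physician cost per intervention patient, the reported saving exceeds the net saving by exactly c, other things equal.

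**2. Reproduce the plan's own cost figure (F1).** Inputs: control mean $7,658, intervention mean $5,169, SD $4,530. F1 gives two-sided 0.05 and 52 per arm for encounters; I take both to apply to costs.
- Difference: 7,658 − 5,169 = $2,489, as stated.
- Power at 52 per arm: 80.0% by the normal approximation and 79.3% by the t-test, against a stated figure above 80%. This is close enough to count as reproduced.
- Expected retained number: 68 × 0.85 = 57.8, about 58 per arm. Power there is 84.1% (normal) or 83.5% (t-test).

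**3. Size of c, by assumption.** The documents give no approval counts, minutes or wages. Table 2 schedules no televisits for low-risk patients, 12 a year for moderate-risk and 24 a year for high-risk patients. Triggered visits are extra and uncounted. Approval attaches to interventions and regimen changes, not to every televisit. Two illustrations, using c = approvals × minutes × cost per minute:
- 6 × 5 × $2.00 = $60; 60 / 2,489 = 2.4% of the planned saving.
- 12 × 10 × $2.50 = $300; 300 / 2,489 = 12.1%.

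**4. What adding the cost would do to planned power.** This applies only if the $2,489 excludes physician time. SD is held at $4,530, with 58 per arm, two-sided 0.05 and the t-test.

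| Uncounted c | Net saving | Power |
|---|---|---|
| $0 | $2,489 | 83.5% |
| $60 | $2,429 | 81.7% |
| $300 | $2,189 | 73.2% |

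By the normal approximation, the smallest saving with 80% power at 58 per arm is 4,530 × √(2/58) × (1.960 + 0.842) = $2,357. The margin is 2,489 − 2,357 = $132, or 5.3% of the planned saving.

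**5. Usual-care contacts.** Let u be uncounted usual-care staff cost per patient. Because both arms get the same usual care, u cancels from the difference unless the intervention changes it. If the intervention lowers u, the omission hides a saving and works against the intervention. If it raises u, the omission flatters the intervention. The documents give no basis for choosing.

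**The case against.** The strongest reply is that the plan is less restrictive than it looks. The intervention-only list is introduced as what costs will include, so it need not be exhaustive. Hospital accounting for all inpatient and outpatient care may already carry the staff cost of visits in both arms. The two gaps may pull in opposite directions. The sizes above rest on assumed counts, minutes and wages.

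Much of this stands, and it limits the point in three ways:
- A reader might infer that the cost comparison is shown to be biased in a known direction. The documents do not support that, since the effect on usual-care contacts is unknown.
- A reader might infer that staff effort cannot be compared at all. That is too strong: visit-related staff cost may be embedded in the accounting data, and usual-care pharmacist visits are documented in the EHR.
- A reader might infer a severe loss of power by giving every patient 24 approvals a year at the longest time and highest wage. That needs the whole arm to be high-risk all year with an approval at every televisit. Leaving a cost out also does not reduce the power of the analysis as planned. Power falls only if the cost is added and F1's saving did not already allow for it, which F1 does not say.

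What the reply does not remove is the physician's time. An open-ended list does not help unless something records the minutes, and no procedure in the protocol does. Embedded visit costs do not cover remote, possibly unbilled, approval.

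**Conclusion.** The point holds in a limited form. C2's staff-effort comparison is not carried through into E4, and a protocol-required input to the intervention is missing from a cost analysis with a declared societal perspective. Through that omission alone, intervention cost is likely understated and the net saving overstated by the value of the physician's time. This assumes that the review is not already captured in hospital accounting.

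The amount cannot be found from the documents; the $60 and $300 cases are illustrations. The direction of the total error is not certain, because it also depends on whether the intervention changes uncounted usual-care contacts. The matter concerns a secondary aim and does not touch the medication-error and adverse-drug-event outcomes. It is worth correcting because the correction is cheap and the cost claim is one of the trial's two hypotheses.

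**What to change.** 1. In E4 item 8, add transplant-physician review and approval time to the intervention costs.
2. For both arms, count logged non-face-to-face staff contacts from the EHR, from randomisation to month 12. Value them at unit times and wages fixed in advance, and include them in total cost. Alternatively, state that usual-care staff cost is already embedded in the accounting data.
3. In F1, state whether the $2,489 saving is net of intervention costs.
4. If steps 1 and 2 are not done, delete staff effort from C2 and label the result as accounting cost plus partial intervention cost.

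The cost is protocol wording, a unit-time table and an EHR extraction at study end. The extraction depends on approvals being logged. D3 describes discussion with providers without saying how it is recorded, so a short log entry may be needed. Unit-time costing approximates staff effort and does not measure it, and the reported saving may turn out smaller than F1 expects.
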